6.5.1.3 Count Outcomes

A generalised linear model (assuming a negative binomial distribution, which accounts for variability among participants in the number of and frequency of the count variable) will be fitted for each count outcome measure with explanatory variables of treatment arm and stratification variables, and log-time on study as an offset. The offset (log-time), allows for different lengths of follow-up time for each participant (Keene et al, 2008). Time on study will be capped at 49 weeks. This assumes that missing data is missing at random (MAR), and will be applied where all of the available observed data are analysed without deletion nor imputation.

The count data is assumed to follow a negative binomial distribution with the over dispersion. If the dispersion is found to be non-significant (i.e no evidence of over-dispersion) we will consider the simpler Poisson model where the dispersion parameter equals to zero. The ratio of the rates (RR) on the intervention arm relative to placebo, associated two-sided 95% confidence interval (CI) and p-value will be reported. A value of 1.0 would indicate the same rate as placebo; the lower the ratio the greater reduction in exacerbations compared with placebo. A two-sided p-value ≤ 0.05 will be considered

as a significant difference in the number of COPD exacerbations in 48 weeks between the two treatment arms.

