2.2.4 Randomisation and blinding

The LCTU will supply a web based randomisation system from a third party (Sealed Envelope Ltd.). Participants will be randomised in a 1:1 ratio to mepolizumab or placebo. The trial team and participants will be blinded to treatment assignment. Randomisation will be stratified on baseline eMRC dyspnoea score (≤ 3 , >3) and past hospitalisation in the previous 12 months (0, ≥ 1).

Each participant will be given a unique trial ID number at randomisation. Randomisation results will be printed out and signed as confirmation by the unblinded trial personnel performing the randomisation and a copy will be stored securely with the unblinded documentation and presented to pharmacy alongside the prescription.

[.....]

Participants, investigators, and all involved in trial conduct, sample analysis, or with any other interest in this trial will remain blind to the randomised treatment assignments until after final analysis is complete. The exception(s) to this are as follows;

- The trial statistician will have access to the web based randomisation database of all randomised participants in order to prepare the unblinded DMC to make safety decisions and complete end of trial analyses.
- The Pharmacy team will be unblinded and have responsibility for storing and dispensing IMP and placebo.
- Unblinded trial personnel from the Respiratory BRC will have responsibility for reconstituting the IMP/placebo and dosing the participants.

[.....]

The treatment allocation will remain blinded to all other trial team members until after database lock.

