3.2 Secondary Outcomes

3.2.1 Definition and Derivation of Secondary Outcomes

Exacerbations and Healthcare Utilisation

- Time from randomisation to next hospital readmission or death due to a respiratory cause

The time from randomisation to next hospital readmission or death (due to a respiratory cause) is defined as a time to event outcome measured in days. The date of randomisation as well as the date of readmission or death due to respiratory causes (whichever occurs first) will be used to calculate time to event. For participants not experiencing an event the time will be calculated from randomisation until last known follow-up assessment event-free. A variable to indicate event (with a value of 1) or no event (with a value of 0) will be derived. Details of the primary outcome analysis are included in section 5.5.

- Total number of hospital readmissions all cause up to 48 weeks

The total number of hospital readmissions (all cause) is defined as a count outcome. The number of hospital readmissions (all cause) in total during the 48 (truncated follow-up

minimum 24) weeks corresponding to each participant will be calculated. Where no hospital admission have occurred a value of zero will be derived.

- Total number of moderate exacerbations up to 48 weeks

The total number of moderate exacerbations is defined as a count outcome. The severity of a COPD exacerbation will be deemed as “Moderate” if the participant required treatment with steroids or antibiotics and was not hospitalised (Oba, Y. et al, 2017).

The number of moderate exacerbations each participant had over the course of 48 (truncated follow-up minimum 24) weeks will be calculated.

- Time from randomisation to treatment failure (defined as the composite of three endpoints: 1. treatment intensification with systemic corticosteroids and/or antibiotics for respiratory reasons; 2. step-up in hospital care for respiratory reasons including transfer to the intensive care unit or readmission; or 3. all-cause mortality)

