6.7 Adjusted Analysis

Modelling of the primary and all secondary outcomes will be adjusted for the baseline eMRC dyspnoea stable state score (≤ 3 , > 3) and past hospitalisation in the previous 12 months (0 , ≥ 1), used as a stratification factor at randomisation.

Adjustment for stratification variables can only take place where the statistical model allows for specification of such variables.

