9.1 Appendix 1: Templates for Tables, Listings and Figures

Table1: Disposition of Patients by treatment arm

	Control, n (%)	Mepolizumab, n (%)	Total, n (%)
Randomised patients			
Completed trial follow-up (End of trial assessment)			
Discontinued due to			
Lost to follow-up			
Withdrawn			
Deaths			
Remained on treatment for intended follow-up period			
Discontinued treatment early			
Reasons:			
Participant decision			
Adverse Event			
Unable to Tolerate Drug			
Participant non-compliance			
Lost to Follow up			
Investigator decision			
Participant Ineligible			
Withdrawn due to Medical Reasons			
Death			
Number of doses received			
1			
2			
3			
4			
5			
6			
7			
8			
9			
10			
11			
12			

Figure 1: A Swimmer plot of participants' discontinuation from the trial with reasons

Table 1: Case Report Form (CRF) return

CRF	Placebo Returned/Expected (%)	Mepolizumab
Visit 1 (Week 0)	Follow-up due	
	Follow-up completed	
Visit 2 (Week 4)	Follow-up due ^a	
	Follow-up completed	
Visit 3 (Week 8)	Follow-up due ^a	
	Follow-up completed	
Visit 4 (Week 12)	Follow-up due ^a	
	Follow-up completed	
Visit 5 (Week 16)	Follow-up due ^a	
	Follow-up completed	
Visit 6 (Week 20)	Follow-up due ^a	
	Follow-up completed	
Visit 7 (Week 24)	Follow-up due ^a	
	Follow-up completed	
Visit 8 (Week 28)	Follow-up due ^a	
	Follow-up completed	
Visit 9 (Week 32)	Follow-up due ^a	
	Follow-up completed	
Visit 10 (Week 36)	Follow-up due ^a	
	Follow-up completed	
Visit 11 (Week 40)	Follow-up due ^a	
	Follow-up completed	
Visit 12 (Week 44)	Follow-up due ^a	
	Follow-up completed	
Visit 13 (Week 48)	Follow-up due ^a	
	Follow-up completed	

^a Will be defined as participants who have passed the visit window stated in the Protocol.

Table 2: Demographic and Baseline Clinical Characteristics

Characteristics	Descriptive	Placebo (n=)	Mepolizumab (n=)	Total (n=)
Age	N			
	Mean [SD]			
	Median [IQR]			
	Min, Max			
Gender	Male			
	Female			

Ethnicity	White
	Asian or Asian British
Smoking status	Current Smoker
	Ex-Smoker
BMI	N
	Mean [SD]
	Median [IQR]
	Min, Max
Number of cigarettes per day	N
	Mean [SD]
	Median [IQR]
	Min, Max
Number of years smoked	N
	Mean [SD]
	Median [IQR]
	Min, Max
Number of emergency admissions (all cause) in previous 12 months	N
	Mean [SD]
	Median [IQR]
	Min, Max
Number of courses of steroids without antibiotics for your chest (COPD exacerbations) in previous 12 months	N
	Mean [SD]
	Median [IQR]

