	Min, Max
Number of courses of antibiotics without steroids for your chest (COPD exacerbations) in previous 12 months	N
	Mean [SD]
	Median [IQR]
	Min, Max
Number of courses of both antibiotics and steroids for your chest (COPD exacerbations) in previous 12 months	N
	Mean [SD]
	Median [IQR]
	Min, Max
Systolic (mmHg)	N
	Mean [SD]
Pre-Dose	Median [IQR]
	Min, Max
Diastolic (mmHg)	N
	Mean [SD]
Pre-Dose	Median [IQR]
	Min, Max
Heart rate (bpm)	N
	Mean [SD]
Pre-Dose	Median [IQR]
	Min, Max
Temperature (°C)	N
	Mean [SD]

Pre-Dose	Median [IQR]
	Min, Max
SpO ₂ (%)	N
	Mean [SD]
Pre-Dose	Median [IQR]
	Min, Max
Respiratory rate (per min)	N
	Mean [SD]
Pre-Dose	Median [IQR]
	Min, Max
Systolic (mmHg)	N
	Mean [SD]
Post-Dose	Median [IQR]
	Min, Max
Diastolic (mmHg)	N
	Mean [SD]
Post-Dose	Median [IQR]
	Min, Max
Heart rate (bpm)	N
	Mean [SD]
Post-Dose	Median [IQR]
	Min, Max
Temperature (°C)	N
	Mean [SD]
Post-Dose	Median [IQR]
	Min, Max
SpO ₂ (%)	N
	Mean [SD]
Post-Dose	Median [IQR]
	Min, Max
Respiratory rate (per min)	N
	Mean [SD]
Post-Dose	Median [IQR]
	Min, Max
eMRC dyspnoea score (stable state)	
2: Breathless when hurrying on the level or walking up a slight hill
 
3: Walks slower than peers or stops when walking on the flat at own pace
 
4: Stops after walking 100m, or for a few minutes, on the level
 
5A: Too breathless to leave the house & independent in washing and/or dressing

	5B: Too breathless to leave the house & dependent in washing and dressing
	Missing*
WHO: Highest level of intervention during baseline admission	No oxygen therapy
	Oxygen by mask or nasal prongs
	Oxygen by NIV or high flow
Time to discharge from index admission (days)	N
	Mean [SD]
	Median [IQR]
	Min, Max
*FEV1, litre	N
	Mean [SD]
	Median [IQR]
	Min, Max
*FEV1, %	N
	Mean [SD]
	Median [IQR]
	Min, Max
*FVC, litre	N
	Mean [SD]
	Median [IQR]
	Min, Max
*FVC, %	N
	Mean [SD]
	Median [IQR]
	Min, Max
*FEV1/FVC ratio, %	N
	Mean [SD]
	Median [IQR]
	Min, Max

Abbreviations: SD= Standard deviation; IQR= Inter-quartile range, Min=Minimum; Max=Maximum; N= number of observations

Data are n (%), mean (SD), or median (IQR), unless otherwise stated.

Figure 2: Proportion of patients in each dose

Figure 3: Number of doses per patient

Figure 4: Kaplan-Meier survival curves of the primary outcome by randomised group

Table 4: Primary Analysis of Primary Outcome: the time from randomisation to next hospital readmission or death (all cause)

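### The count models for moderate exacerbations and readmissions could gain precision, at almost no cost, by adjusting for the previous-12-month counts that the trial already records

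*SAP*

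**What the plan says.** SAP 6.5.1.3 describes one negative binomial model for both count outcomes, which "will be fitted for each count outcome measure with explanatory variables of treatment arm and stratification variables, and log-time on study as an offset". SAP 6.5.2 repeats the model in the per-protocol population with time on treatment as the offset.

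SAP 6.7 sets the adjustment rule: "Modelling of the primary and all secondary outcomes will be adjusted for the baseline eMRC dyspnoea stable state score", dichotomised at 3, together with "past hospitalisation in the previous 12 months", coded 0 or ≥1. Protocol 10.5 gives the same rule. Neither document names any other covariate for the counts.

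SAP 3.2.1 calls an exacerbation moderate if the participant "required treatment with steroids or antibiotics and was not hospitalised".

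The demographic and baseline table in SAP Appendix 1 lists these items as numbers:
- "Number of emergency admissions (all cause) in previous 12 months"
- "Number of courses of steroids without antibiotics for your chest (COPD exacerbations) in previous 12 months"
- "Number of courses of antibiotics without steroids for your chest (COPD exacerbations) in previous 12 months"
- a matching item for courses of both drugs together.

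For continuous longitudinal outcomes, SAP 6.5.1.2 includes the baseline value as a fixed effect.

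**The concern.** Participants differ in their underlying event rate, and SAP 6.5.1.3 chooses the negative binomial distribution for that reason. A participant's event count in the year before entry is a natural predictor of that rate. Leaving it out sends any heterogeneity it would explain into the dispersion parameter, which widens the interval for the rate ratio. It also leaves chance imbalance in exacerbation history between arms uncorrected.

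The gap differs between the two outcomes. For moderate exacerbations, no measure of prior steroid or antibiotic treatment enters the model. For readmissions, one prior admission is treated the same as six.

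The plan is also uneven within itself. Continuous outcomes get a baseline covariate and counts do not. SAP 6.5.3 lists a baseline value among the imputation predictors for key secondary outcomes, which include both counts and SGRQ, but no baseline value is defined for a count.

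At stake is the precision of two secondary efficacy comparisons, each judged at a two-sided 0.05 level.

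**Working it through.** **1. The plan's own sample size.** SAP 2.2.3 assumes 65% control events, a hazard ratio of 0.6, 80% power and α = 0.05.
- Freedman events: [(1 + 0.6)/(1 − 0.6)]² × (1.960 + 0.842)² = 16 × 7.849 = 125.6, so 126.
- Mepolizumab event proportion: 1 − 0.35^0.6 = 46.7%. Mean of the two arms: 55.9%.
- N = 126/0.5587 = 225.5, so 226. With 5% drop-out, 226/0.95 = 237.9, so 238.

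The stated 226 and 238 reproduce. They concern the primary time-to-event outcome. No power is stated for either count outcome.

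**2. Closed form for a count outcome.** Let n be participants per arm, t follow-up in years, r the placebo rate, RR the rate ratio and k the dispersion. Then

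Var(log RR) = [1/(r t) + 1/(r RR t) + 2k] / n, and power ≈ Φ(|log RR|/SE − 1.96).

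From the documents: n = 113 and t = 48/52 (full follow-up). Assumed for illustration: r = 1.5 per year, RR = 0.6, k = 0.8. The first two terms are 0.722 and 1.204.

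| Share of k explained by the prior count | k left | Var(log RR) | SE | Power |
|---|---|---|---|---|
| none (as planned) | 0.80 | (0.722 + 1.204 + 1.60)/113 = 0.0312 | 0.177 | 82.4% |
| 10% | 0.72 | (0.722 + 1.204 + 1.44)/113 = 0.0298 | 0.173 | 84.1% |
| 30% | 0.56 | (0.722 + 1.204 + 1.12)/113 = 0.0270 | 0.164 | 87.5% |
| 50% | 0.40 | (0.722 + 1.204 + 0.80)/113 = 0.0241 | 0.155 | 90.8% |

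At 30%, the variance falls by about 14% (0.0270/0.0312 = 0.864). That is worth about 36 extra participants (226/0.864 ≈ 262). Across a wider grid of assumptions, the closed form gives 0.4 to 3 points for a 10% cut in k, 1 to 10 for 30% and 2 to 19 for 50%. It ignores the binary hospitalisation factor, so it overstates the gain for readmissions.

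**3. Simulation with the planned covariates.** Negative binomial models were fitted to large simulated data sets (60,000 participants, standard errors rescaled to 226). Prior and on-trial rates were lognormal with log-rate correlation ρ, and about one sixth of participants had truncated follow-up. All of the following are assumptions:
- rate heterogeneity 0.5 to 1.5 and RR 0.6 to 0.8
- moderate exacerbations at a mean of 1 to 2 per year
- readmissions at a mean of 1.27 to 1.71 per year, set so that 64% have an event in 12 months (the Leicestershire figure in SAP 2.2.3).

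The readmission model already held prior hospitalisation as 0 / ≥1. The added term was log(count + 0.5).

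| ρ | Gain, moderate exacerbations (points) | Gain, readmissions beyond the binary factor (points) |
|---|---|---|
| 0.3 | about 0 to 1 | about 0 to 1 |
| 0.5 | 0 to 3 | 0 to 2 |
| 0.7 | 1 to 8 | 0.5 to 5 |
| 0.9 | 1 to 12 | 1 to 9 |

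Both maxima came at heterogeneity 1.5, RR 0.7 and ρ = 0.9. Power rose from 53.5% to 65.6% for moderate exacerbations (mean 2.0) and from 53.2% to 62.5% for readmissions (mean 1.71). Simulation noise in a gain is about 1 point or less.

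The moderate-exacerbation runs gave no credit to the hospitalisation split, which is in the planned model and may carry some information on exacerbation rate. On that count, those figures lean high.

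**4. Further fits.** At rates of 1.5 to 2 per year, dispersion 0.8 to 1.2, RR 0.65 and ρ from 0.5 to 0.9, the gain was about 2 to 10 points with no history in the model and about 1 to 7 points beyond a binary history factor. Both sit inside the ranges above.

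**The case against.** The strongest reply is that this is a preference for efficiency and not a fault. Adjusting every outcome for the stratification factors is a deliberate rule stated in both documents. A negative binomial model with a follow-up offset accommodates over-dispersion and gives a valid estimate and interval without further covariates. The outcomes are secondary and carry no power target. All of that stands, and it limits the point to an optional improvement.

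Three further objections also stand in part.
- **The baseline items are proxies.** A reader might take them as the same events as the outcomes. They are treatment courses, with no stated exclusion of courses given during an admission, whereas an on-trial moderate exacerbation excludes hospitalised events. The admission item covers emergency admissions only. A proxy can still predict, but imperfect overlap pulls the correlation down.
- **The parallel with continuous outcomes is loose.** Those baselines are the same instrument repeated, and SAP 6.5.1.2 itself gives up baseline adjustment if it falls back to a rank test.
- **Missing values need care.** SAP 6.5.1.3 commits to analysing all observed data with no one removed and nothing imputed. A covariate with gaps would breach that unless a rule is written.

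A reader might also infer that the readmission model ignores history altogether. It does not: past hospitalisation is both a randomisation stratum and a covariate. Only the information above the yes/no split is lost, and stratification already limits imbalance on that split.

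**Conclusion.** The omission is confirmed from the documents, and adding the counts would normally improve precision. The planned models remain valid, and no stated figure in the plan is wrong.

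The size cannot be derived from the documents. Under the assumptions shown, the gain is roughly 0 to 12 points of power for moderate exacerbations and 0 to 9 points for readmissions beyond the binary factor. It can be near zero. Gains of 3 points or more generally need a log-rate correlation of about 0.7 or higher and substantial over-dispersion.

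A reader might infer a firm loss of, say, 3 to 16 points for both outcomes. The material does not support that. Gains near 16 points appear only in the closed form, with dispersion of 1.0 or more cut by about half, and not for readmissions once the binary factor is in the model. One range should not cover both outcomes. The case is strongest for moderate exacerbations.

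**What to change.** Before database lock, amend SAP 6.5.1.3, carry the change into 6.5.2, and add a line to 6.7:
- **Moderate exacerbations:** add log(1 + total of steroid-only, antibiotic-only and combined courses in the previous 12 months).
- **Readmissions:** add log(1 + emergency admissions in the previous 12 months).
- Keep both stratification factors and the offset in each model.
- **Missing baseline count:** state a rule that drops no participant, for example single imputation of the pooled-arm median with a missing indicator. Make clear that this fills a baseline covariate and leaves the outcome unimputed.
- Say whether these counts are the baseline value meant for the count outcomes in the SAP 6.5.3 imputation.

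Record the change in SAP 6.8 and in the summary-of-changes table that Protocol 10.3 requires. Fix the covariate form in advance, because the trial statistician has access to allocation and a choice made after seeing results by arm would be data-driven.

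The cost is one term per model and one missing-data sentence, with no new data collection. The downside is small: the covariates are proxies and may explain little. The calculation used log(count + 0.5). The recommended log(1 + count) is a similar transform but was not run separately on that grid.

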10.3.3 Secondary outcome analysis

All secondary end-points will be analysed using the ITT population, with the exception of adverse events, for which we will analyse the safety population, consisting of all participants who received at least one dose of trial medication. The count outcomes, number of hospital readmissions and number of moderate exacerbations over 48 weeks, will be analysed using the per protocol (PP) population where patients will be included in the analysis if they have a received a minimum duration of trial treatment of 24 weeks.

All time to event secondary outcomes will be analysed the same way as the primary outcome.

All count secondary outcomes, number of hospital readmissions and number of moderate exacerbations, will be analysed using a negative binomial regression model. If there is no evidence of over-dispersion, a Poisson regression model will be used in place.

All binary secondary outcomes will be compared between treatment groups using logistic regression.

All continuous longitudinal outcomes (repeated measurements) will be compared using mixed effects model with patient as a random effect to account for repeated measures over time. This method will enable handling of missing data within the follow-up visits.

This trial has a single primary outcome, therefore there will not be a formal adjustment for multiple significance testing.

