2.2.3 Sample size

Readmission rates at 6, 9 and 12 months were 51%, 59% and 64% respectively for patients admitted with a diagnosis of COPD (ICD code: J44) in Leicestershire in 2015. This is in line with national data from the HQIP RCP National COPD audit (2014) which had a readmission rate of 43% at 3 months. In addition, 6% of patients discharged from hospital with an exacerbation of COPD died in the 12 months following admission without hospital readmission.

National UK data from the HQIP funded RCP/BTS National COPD audit (2014; data unpublished) showed 24.9% patients had an eosinophil count of ≥ 300 cells/ μL on admission. In patients with an eosinophil of ≥ 300 cells/ μL on admission ($n=1,587$), 46.1% of patients were readmitted within 3 months of initial hospitalisation, similar to the non-eosinophilic COPD population.

Assuming 65% of patients receiving usual care will have an event by 48 weeks (composite endpoint: hospitalisation or death) and those treated with mepolizumab have a hazard ratio of 0.6, then 226 patients (113 per group) would be required to show a statistical difference power 0.8, $\alpha=0.05$). We have also assumed 5% drop-out (recruited but not receiving first dose) and therefore the final recruitment target of 238 patients.

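### A non-significant dispersion test moves the count outcomes from negative binomial to Poisson; if over-dispersion is weak or events are few this narrows the interval slightly, and the switch can be deleted at almost no cost.

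*SAP*

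**What the plan says.** SAP 6.5.1.3 starts from a negative binomial model: "The count data is assumed to follow a negative binomial distribution with the over dispersion". Treatment arm and the stratification factors are covariates, and log time on study is the offset: "The offset (log-time), allows for different lengths of follow-up time for each participant". The result is a rate ratio with "associated two-sided 95% confidence interval (CI) and p-value will be reported". The section then adds the escape: "If the dispersion is found to be non-significant (i.e no evidence of over-dispersion) we will consider the simpler Poisson model".

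Protocol 10.3.3 states the rule more firmly: "If there is no evidence of over-dispersion, a Poisson regression model will be used in place". SAP 6.5.1 repeats that sentence. So one section promises only to consider Poisson, while two others require it.

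SAP 6.5.2 carries the same methods into the per-protocol set for both count outcomes. None of these sections names the dispersion test or its significance level, and none mentions a robust or scaled standard error for the Poisson fit.

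**The concern.** A dispersion test that fails to reach significance leaves a range of dispersion values open, yet the rule then fits a model that fixes dispersion at zero. If some over-dispersion is present, the Poisson standard error is too small, and the interval and p-value are too favourable in exactly the trials where the test missed it. The negative binomial already contains the Poisson as its limit, so little is gained by switching when the data really are Poisson.

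The SAP is wary of this kind of reasoning elsewhere: its sections 5 and 6.5.1.2 caution against relying on formal normality tests.

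Two outcomes that SAP 6.5.3 treats as key secondary are affected. Because the wording differs in force and no test is named, the final model for a borderline dispersion is not fixed in advance. The main and per-protocol analyses could end up with different models. SAP 6.5.3 adds 50 imputations for these counts without saying how a dispersion test made in each imputed data set would be resolved.

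**Working it through.** **Sample size used.** The plan gives no calculation for the counts, so the primary-outcome size is taken. Inputs, from SAP 2.2.3: "Assuming 65% of patients receiving usual care will have an event by 48 weeks"; "those treated with mepolizumab have a hazard ratio of 0.6"; power 0.8; two-sided 0.05.
- Freedman events: [(1+0.6)/(1−0.6)]² × (1.960+0.842)² = 16 × 7.85 ≈ 126.
- Mepolizumab event probability: 1 − 0.35^0.6 = 0.467.
- Per group: 126/(0.65+0.467) = 112.8, so 113 and 226 in total. This matches "226 patients (113 per group) would be required to show a statistical difference power 0.8". Then 226/0.95 = 237.9, giving 238.

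**Assumptions for the counts.** Dispersion k and mean μ per 48 weeks are not stated, so both are varied. The share with truncated follow-up is not stated; 20% is assumed, with 24 to 44 weeks each. The test is a likelihood ratio at the one-sided boundary cut-off (2.71). Stratification covariates are left out. In the first four rows μ is set so that 64% have at least one event: μ = (0.36^(−k) − 1)/k. The last three rows take a low mean of 0.5.

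**Results at N = 226, no treatment effect, 5,000 runs per row** (Monte Carlo error about 0.3 points; paired differences are more precise):

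| μ | k | Switches to Poisson | Poisson SE / fitted NB SE if switched | Type I error if switched | Type I, rule | Type I, NB always |
|---|---|---|---|---|---|---|
| 1.076 | 0.1 | 76% | 0.971 | 6.4% | 5.8% | 5.1% |
| 1.134 | 0.2 | 41% | 0.959 | 6.9% | 5.5% | 5.2% |
| 1.196 | 0.3 | 13% | 0.950 | 9.1% | 5.6% | 5.4% |
| 1.333 | 0.5 | 0.3% | 0.938 | too few | 5.3% | 5.3% |
| 0.5 | 0.3 | 66% | 0.967 | 5.8% | 5.2% | 4.8% |
| 0.5 | 0.5 | 38% | 0.958 | 8.0% | 6.1% | 5.7% |
| 0.5 | 0.8 | 11% | 0.951 | 8.8% | 5.5% | 5.2% |

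Separate runs with μ fixed at 1.0 and k = 0.1/0.2/0.3 switched in 77/46/20% of trials at 113 per arm and 77/43/17% at 119 per arm. With the 3.84 cut-off instead of 2.71, switching is somewhat more frequent and the overall excess is at most about 0.9 points.

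**Smaller per-protocol set.** Its size is not given; 150 is assumed. At the 64% mean, k = 0.3 is missed in 27% of trials and k = 0.5 in 1%. These rows have only 1,000 runs. The largest overall excess among them at the 2.71 cut-off was 7.6% against 6.4% (k = 0.2), or 12 extra rejections in 1,000.

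**What the plan's own rates imply for readmissions.** Under a constant-rate negative binomial, the probability of no readmission by fraction t of a year is (1 + kμt)^(−1/k). Setting this to 0.49 at t = 0.5 and 0.36 at t = 1 (51% and 64% readmitted, SAP 2.2.3) gives k ≈ 1.74 and μ ≈ 2.8. At t = 0.75 it predicts 58.9% readmitted, against 59% stated. By contrast, k = 0.1 to 0.3 with 64% at 12 months predicts only 41 to 42% at 6 months, against 51% stated. At k = 1.74 the dispersion test was significant in all 4,000 runs (N = 226 or 150), so the switch never occurred.

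**Cost of never switching.** With truly Poisson data, power under the negative binomial throughout was 70.3% against 70.9% under the rule (μ = 1.0, rate ratio 0.7). At μ = 0.5 and rate ratio 0.6 it was 67.3% against 68.0% (3,000 runs each).

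**The case against.** The best defence is that the rule limits its own harm. Over-dispersion strong enough to matter is detected: at the 64% mean, 0.3% of trials miss k = 0.5 and none miss k = 0.8. What is missed is weak, or occurs where events are few, and there the two models give similar intervals. The fallback is prespecified, these are secondary outcomes without multiplicity control, and a shift of under a point would not change how they are read. All of this stands and sets the priority.

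Three stronger readings are tempting but not supported:

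- A reader might infer that the test will often miss real over-dispersion in this trial. That needs weak dispersion or a low event rate, which the documents neither state nor, for readmissions, suggest.
- A reader might take 1/√(1+kμ) at μ = 1.0, which is 0.953, 0.913 and 0.877 for k = 0.1, 0.2 and 0.3, to mean that reported intervals would be 5, 9 and 12% too narrow. That compares Poisson with the standard error under the true dispersion. Trials that switch have low estimated dispersion by selection, so the negative binomial fit they would otherwise report differs by only about 3 to 7%.
- Forcing Poisson at k = 1.74 gives about 40% type I error, but the rule would not choose Poisson there.

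What survives is that the step gains almost nothing when it is right, narrows the interval when it is wrong, and is worded in two different strengths.

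**Conclusion.** The point holds as a minor, nearly free improvement. If over-dispersion is weak (k about 0.1 to 0.3 at a mean of 1.0) or events are few (mean 0.5, k up to about 0.5), the switch would occur in a substantial share of trials. The Poisson standard error would be about 3 to 7% below the fitted negative binomial one, and type I error among switched trials about 6 to 9%. Overall inflation is under 1 percentage point at N = 226, and roughly 1 point in an assumed per-protocol set of 150, where the estimate is less precise.

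Readmissions are probably unaffected. That rests on reading the falling readmission rate as variation between patients; if the hazard truly falls over time, k is below 1.74. The rates also come from a general COPD admission cohort, not from trial participants. Moderate exacerbations are the open case, since no rate or dispersion is given for them. The primary analysis is untouched.

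One limit on the stakes: SAP 6.5.1.3 ties its 0.05 threshold to the number of COPD exacerbations, so it should not be read as a declared significance rule for both count outcomes.

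**What to change.** Before database lock, delete the switch in Protocol 10.3.3, SAP 6.5.1 and SAP 6.5.1.3. All three need editing: leaving the sentence in SAP 6.5.1 would still order the substitution. SAP 6.5.2 then follows without change. State that the negative binomial model is fitted whatever a dispersion test shows, and that Poisson with robust standard errors is used only if the negative binomial fails to converge because the dispersion estimate is at zero. Apply the same statement to the imputed data sets in SAP 6.5.3.

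This also removes the conflict between considering and requiring Poisson. The cost is a text edit, with no extra data, and under 1 point of power in the scenarios run if the counts are truly Poisson.
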